#### **11.6** VITAL SIGNS

Vital signs will consist of blood pressure (systolic and diastolic blood pressure, mmHg), pulse rate (beats per minute), and respiratory rate (breaths/min). Vital sign values and change from baseline in the vital signs will be summarized for each treatment group.

#### **11.7** PHYSICAL EXAM

Number and percent of subjects with abnormal physical exam findings at Screening will be summarized by body system for each treatment group and overall. Physical Exam data for each subject will also be presented in a listing.

#### **11.8** 12-LEAD ELECTROCARDIOGRAM (ECG)

12-Lead ECGs will be performed over time. The ECG variables will include ventricular heart rate and the PR, QRS, QT, QTcB and QTcF intervals. The ECGs will be signed and dated by a medically-qualified individual to confirm review of the ECG and verify whether any abnormalities are clinically significant.

Number and percent of subjects in each ECG finding category (normal, abnormal not clinically significant, and abnormal and clinically significant), will be summarized for each visit by each treatment group and overall. Summary statistics will be presented for the actual value and actual change for each ECG parameter.

The number and percent of subjects with QT, QTcB and QTcF intervals < 450 msec, 450 to <480, 480 to <500 and greater than/equal to 500 msec at each visit and overall (at any visit) will be summarized. Additionally, the number and percentage of subjects with changes in these parameters of <30 msec, 30 to <60 msec and greater than/equal to 60 msec will be summarized at each visit and overall at the visits where ECG is scheduled).

Buprenorphine plasma concentration vs QT, QTcB and/or QTcF interval relationships will be graphically graphically explored.

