All efforts should be made by the Investigator to continue collection of concomitant medications, and AEs in subjects that discontinue study drugs, unless the subject withdraws his/her consent at the time of early discontinuation. Subjects discontinued due to clinically significant QTc interval prolongation should be monitored closely by undergoing daily ECGs, until ECG readings return to baseline, or QTc interval values are no longer judged to be clinically significant. The Investigator should also ask the subject to complete the Follow-up phone-call, provided that the subject has not withdrawn consent. If a subject refuses to complete EOT procedures and/or Follow-up, this information will be recorded.

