#### Table 1: Schedule of Assessments – Group 1 (CAM2038 q1w) Campulation

a Subjects must voluntarily provide written informed consent prior to any study-related procedures being performed.

b Prior to treatment on Day 1, all Inclusion and none of the Exclusion criteria must be met.

c Vital signs (temperature, blood pressure, pulse rate, respiratory rate) will be measured pre-dose and 15 minutes' post-dose after each CAM2038 q1w administration and will be measured once at each non-dosing visit.

d ECG will be measured at the Screening and EOT visits, and pre-dose and 23 (±2) hours after the first CAM2038 q1w administration. ECGs will be measured at 1, 4, 6, 10, 24, 48, 72, 96 and 168 hours post-dose on doses 4 through 7.

e Assessment of serum sodium, bicarbonate, potassium, magnesium, calcium levels only.

 $^{\rm f}$  A serum pregnancy test will be performed at Screening and EOT visits. An "in-office" urine pregnancy test will be required prior to all doses of CAM2038 q1w (for women of childbearing potential) during days 1 through 50. An "in-office" urine pregnancy test will be required prior to all doses of CAM2038 q1w (for women of childbearing potential) for those women who continue in the extension phase will also be required.

g Any spontaneously reported AEs will be recorded after the subject signs the ICF. In addition, AEs will be elicited using a non-leading question each time the subject visits the clinic and once daily during inpatient stays.

Version: 5.0, 05 OCT 2016

Page 38 of 87

п5-15-549													 ΜΥΓΙ	DENT.	IAL
Study Period/Phase:	Screening			Tre	atment	Phase		Op	en-lab	el Sa	fety E	xtensi	on Pl	iase	
Treatment:				C	AM2038	8 q1w		CAM2038 q1w							FU
CAM2038 q1w Dose:			Doses	1 to 3		Da	oses 4 to 7	Doses 8 - 13							1
Day:	-21 to -1	D1	D2	D8	D15	D22, D29 D36,	D23-27, D30- 34, D37-41, D44-48	D50/ EOT	D57	D64	D71	D78	D85	D92/ EOT	D99 / FU
C-SSRS h	Х	Х	X	Х	Х	Х		X			X			X	
Injection Site Examination 		Х	X	Х	Х	Х	X	X	X	X	X	Х	X	X	
PK samples		X j		X j	Xj	Х	X k	X k						X	
cows 		Х	X	X	Х	Х		X						X	
sows 		Х	X	X	Х	Х		X						X	
UDS and Breath Alcohol Test	Х	Х	X	Х	Х	Х	X	X			X			X	
NRS for Pain m	Х	Х	X	Х	Х	Х	X	X	X	X	X	Х	X	X	
Randomization n		Х													
CAM2038 q1w SC injection 		X		X	Х	Х		X	X	X	X	X	X		

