#### Table 2: Schedule of Assessments – Group 2 (128 mg CAM2038 q4w) Page 2 (128 mg CAM2038 q4w)

a Subjects must voluntarily provide written informed consent prior to any study-related procedures being performed.

b Prior to treatment on Day 1, all Inclusion and none of the Exclusion criteria must be met.

c Vital signs (temperature, blood pressure, pulse rate, respiratory rate) will be measured pre-dose and 15 minutes post-dose after each CAM2038 q4w administration. Vital signs will also be measured at the Screening, Day 2 and EOT visits, and at each admission.

d ECG will be measured at the Screening and EOT visits, and pre-dose and 6 (±1) hours after each CAM2038 q4w administration. After dose 4, ECGs will be measured at 1, 4, 6, 10, 24, 72, 120, 168 (7 days), 336 (14 days) and 672 (28 days) hours post-dose.

e Assessment of serum sodium, bicarbonate, potassium, magnesium, calcium levels only.

f A serum pregnancy test will be performed at Screening and EOT visits. An "in-office" urine pregnancy test will be required prior to all doses of CAM2038 q4w (for women of childbearing potential) during days 1 through 113. An "in-office" urine pregnancy test will be required prior to all doses of CAM2038 q1w (for women of childbearing potential) for those women that continue to the extension phase.

Clinical Study Protocol Braeburn Pharmaceuticals HS-15-549 g Any spontaneously reported AEs will be recorded after the subject signs the ICF. In addition, AEs will be elicited using a non-leading question each time the subject visits the clinic and once daily during inpatient stays.

Study Period/Phase:	Screening	Treatment Phase											Open-label Safety Extension Phase							
Treatment:					12	28 mg	CAN	A2038	8 q4w				CAM2038 q1w							
CAM2038 q4w Dose:		1	Dose	1	Do	se 2	Do	se 3		D	ose 4									
Day:	-21 to -1	D1	D2	D8 D15 D22	D29	D31 D36 D43 D50	D57	D59 D64 D71 D78	D85	D86	D87, D88 D89, D90 D92, D95 D99, D106	D113/ EOT	D120	D127	D134	D141	D148	D155/ EOT	D162	
C-SSRS h	X	X	Х		Х		X		X			Х			X			X		
Injection Site Examination 		X	Х	X	X	X	X	Х	X	X	Х	Х	X	Х	X	X	X	X		
PK samples		Xj		хj	Xk	X k	X k	X k	X l	X	X m	Х						X		
cows n		X	Х		Х		X		X			Х						X		
sows n		X	Х		Х		X		X			Х						X		
UDS and breath alcohol test	X	X	Х	X	Х	Х	X	Х	X	Х	Х	Х			X			X		
NRS for Pain 	X	X	Х	X	Х	Х	X	Х	X	Х	X	Х	X	X	X	X	X	X		

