### 10.7 Appropriateness of Measures

The primary objective of this study is to evaluate steady state PK of CAM2038 q1w following SC injection at various administration sites and steady state PK of CAM2038 q4w; therefore, PK

Clinical Study Protocol Braeburn Pharmaceuticals HS-15-549 CONFIDENTIAL blood samples will be collected to assess plasma concentrations of BPN and norBPN and derive the necessary PK parameters to evaluate rate and extent of exposure.

Standard safety outcomes, such as AEs, vital signs and clinical laboratory testing will be assessed during the study. In addition, frequent ECG assessments will be included to monitor potential QTc interval prolongation following repeated administration of CAM2038 q1w and q4w. The COWS and SOWS are included to monitor any potential opioid withdrawal symptoms associated with transitiong from SL BPN to CAM2038 and throughout the study.

Exploratory measures include urine toxicology and pain NRS scores, which are typical of studies evaluating efficacy in managing opioid dependence and chronic pain.

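### SAP 11.8 gives the two QTc outlier tables different scopes: the overall change row covers only visits with a scheduled ECG, and no rule covers visits with several timed ECGs

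*SAP*

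**What the plan says.** SAP 11.8 plans three categorical ECG summaries: a finding category (normal, abnormal not clinically significant, abnormal clinically significant) for each visit, absolute interval categories, and change categories.

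- **Absolute categories** (below 450, 450 to <480, 480 to <500, 500 msec or more): "at each visit and overall (at any visit) will be summarized".
- **Change categories**: "changes in these parameters of <30 msec, 30 to <60 msec and greater than/equal to 60 msec". These "will be summarized at each visit and overall at the visits where ECG is scheduled". The sentence closes a parenthesis that it never opened.

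None of these tables names a post-dose time. The sentence on numeric summary statistics names neither a visit nor a time.

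The protocol times ECGs within the day. For Group 1, Table 1 footnote d says: "ECGs will be measured at 1, 4, 6, 10, 24, 48, 72, 96 and 168 hours post-dose on doses 4 through 7". For Group 2, Table 2 footnote d sets ECGs "pre-dose and 6 (±1) hours after each CAM2038 q4w administration", with a denser series after dose 4. Table 3 does the same for Group 3.

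Protocol 10.5.5 discontinues a subject whose QTc exceeds 500 msec or rises by more than 60 msec, and then requires daily ECGs. Section 8.3 says that subjects discontinued for clinically significant QTc prolongation "should be monitored closely by undergoing daily ECGs". Those ECGs are not in the visit schedule.

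**The concern.** Two adjacent tables on the same intervals should have the same reach unless a reason is given, and none is. The narrower table is the one that mirrors the protocol's own 60 msec criterion. A subject withdrawn for an increase above 60 msec could be counted in the disposition table and be absent from the row for 60 msec or more.

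The second part concerns the unit of summary. Protocol 10.7 explains the ECG schedule this way: "frequent ECG assessments will be included to monitor potential QTc interval prolongation". The readings are spread over the dosing interval for that purpose. If the tables recognise only visits, the programmer must choose which of several same-day readings counts, and that choice can move a subject between categories.

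**Working it through.** The documents give no computed figure on this point, so the check is a comparison of text, a count of ECGs and two labelled illustrations.

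**1. Scope of the overall rows.** Absolute: any visit. Change: visits where an ECG is scheduled. If the stray parenthesis means that the last phrase was a gloss on the word overall, the limit is the same.

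**2. Where an ECG can fall outside the change row.**

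- Visits with no scheduled ECG in Tables 1 to 3: Group 1 Days 8 and 15; Group 2 Day 2; and in Group 3 Day 9, Days 15, 22 and 29, Days 38, 43, 50 and 57, and Days 66, 71, 78 and 85. The Group 3 total is 1 + 3 + 4 + 4 = 12 visits. Day 9 is the visit that checks the transition to the depot.
- Daily ECGs after a QTc discontinuation. Most follow a rise that has already been counted. They add a subject only when the first trigger was not itself a change of 60 msec or more. For example, 500 − 60 = 440, so a subject with a baseline above 440 msec can pass 500 msec with an increase below 60 and rise further on a daily ECG.

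**3. Whether the absolute table covers the gap.** Illustration with assumed values: baseline 380 msec, change +65 msec. 380 + 65 = 445 msec, which lies in the category below 450. The change table is the one that would flag this subject.

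**4. Timed ECGs on one day**, counted from footnote d of Tables 1 to 3:

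| Group | Day | Readings | Count |
|---|---|---|---|
| 1 | 22 | 1, 4, 6, 10 h | 4 |
| 1 | 29, 36, 43 | 168 h of the previous dose; 1, 4, 6, 10 h | 5 |
| 2 | 1, 29, 57 | pre-dose, 6 h | 2 |
| 2 | 85 | pre-dose, 1, 4, 6, 10 h | 5 |
| 3 | 8, 36, 64 | pre-dose, 6 h | 2 |
| 3 | 92 | pre-dose, 1, 4, 6, 10 h | 5 |

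**5. Whether the within-visit choice matters.** Illustration with assumed values: one of five readings at +65 msec and four at +20.

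- Maximum: +65, category 60 or more.
- Mean: (65 + 4 × 20) / 5 = 145 / 5 = +29, category below 30.

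A simulation of one five-ECG visit compared three rules. Its assumptions were between- and within-subject SDs both 8, 10 or 12 msec, a peak effect of 10 to 30 msec, and readings at 0, half, full, full and half of the peak. The share of subjects at 60 msec or more was 0.04 to 12.6% by maximum, 0 to 0.9% by mean and 0 to 1.5% by last value. No document supplies these SDs or effects. The ranges show only that the rule matters.

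**6. Weight of one subject.** 1/16 = 6.25% (Groups 2 and 3). 1/24 = 4.2% and 1/20 = 5.0% (Group 1).

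**The case against.** A reader might infer that unscheduled prolongations go uncounted altogether, and that timed ECGs are pooled so that the peak is diluted. The documents support neither reading. The absolute table reaches any visit, and Protocol 12.3.3 promises by-subject listings of all safety data. The SAP contains no averaging rule for post-baseline ECGs: the averaging in SAP 6.1 is for baseline only, and SAP 11.8 is silent.

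More can be said for the plan. The restriction is on visits, so a repeat ECG at a visit with a scheduled one is not excluded. Groups 1 and 2 have few visits without an ECG. Early discontinuers have end-of-treatment assessments, which include an ECG. Reasons for discontinuation are tabulated (SAP 7.1), and SAP 11.8 plans plots of concentration against QTc. The study is a small open-label PK study, and SAP 11.0 makes formal safety comparisons post hoc.

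All of this stands, and it limits the point. It does not remove the mismatch. A listing or a plot is not an outlier count, and a discontinuation reason does not give the size of the change. The missing within-visit rule would be a minor clarification on its own. It belongs here because the same rewrite settles it.

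**Conclusion.** The point holds in a limited form. As worded, the overall change row of SAP 11.8 is narrower than the absolute row beside it and can omit a change of 60 msec or more seen only outside scheduled-ECG visits. The number affected is probably small: it needs an ECG at one of the visits in step 2, or a later rise on a daily follow-up ECG. In groups of 16 to 24, though, one subject decides whether the row reads zero.

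The outlier and finding-category tables also lack a rule for days with up to five ECGs. That is an omission; it is not a stated decision to merge readings, and any figure for dilution depends on a rule that the SAP does not contain. No PK result is affected. The conclusion rests on reading the sentence in SAP 11.8 literally.

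**What to change.** In SAP 11.8:

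- Base the overall rows of both tables on each subject's maximum post-baseline value and maximum change, over all ECGs, scheduled and unscheduled.
- On intensive ECG days, summarise by dose number and nominal post-dose time, as SAP 10.3 already does for plasma concentrations.
- Where a visit-level category is kept, state that the worst value at that visit is used.

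This needs no new data or procedures and touches no clinical rule. It costs some table programming and longer ECG tables, and the outlier percentages may come out slightly less favourable.

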#### **11.9** INJECTION SITE EXAMINATION

All CAM2038 injection sites (new and old) will be examined during each scheduled visit after the first dose of CAM2038 for any signs of adverse site reactions, including erythema, pruritus, edema, pain, etc. Injection site examination form is included in Appendix 17.3 of the protocol. Subjects will also be queried specifically about local tolerability AEs in connection to the examinations.

AEs that believed to be associated with injection procedures will be summarized similarly to the summaries for other AEs (not associated with injections).

# **12.0** IDENTIFICATION AND SUMMARY OF PROTOCOL DEVIATIONS

Major protocol deviations from entry criteria and treatment compliance will be summarized as far as they can be extracted from numeric or coded study data.

# **13.0** DATA QUALITY ASSURANCE

Accurate and reliable data collection will be ensured by verification and cross check of the CRFs against the investigator's records by the study monitor (source document verification) and by the maintenance of a drug–dispensing log by the investigator. Collected data will be entered into a computer database and subject to electronic and manual quality assurance procedures.

## 14.0 REFERENCES

None.

# **15.0** APPENDICES

# **15.1** APPENDIX A - IMPUTATION ALGORITHM FOR PARTIAL AND MISSING DATES

This section describes missing date imputation methods.

#### For Adverse Events

If onset date is completely missing, onset date is set to date of randomization.

If (year is present and month and day are missing) or (year and day are present and month is missing):

- If year = year of randomization, then set month and day to month and day of randomization
- If year < year of randomization, then set month and day to December 31.
- If year > year of randomization, then set month and day to January 1.

If month and year are present and day is missing:

- If year=year of randomization and
  - If month = month of randomization then set day to day of first dose
  - If month < month of first dose then set day to last day of month
  - If month > month of first dose then set day to first day of month
- If year < year of randomization then set day to last day of month
- If year > year of randomization then set day to first day of month

For all other cases, set onset date to date of randomization.

- Concomitant Medications/Medical History
- For start date
- If start date is completely missing, start date will not be imputed.
- If (year is present and month and day are missing) or (year and day are present and month is missing), set month and day to January 1.
- If year and month are present and day is missing, set day to 1st day of month.

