# 7 INVESTIGATIONAL PLAN

## 7.1 Overall Study Design and Plan

This is a Phase II, open-label, partially randomized, 3-treatment group study designed to evaluate the steady state PK of BPN and norBPN following multiple weekly SC administrations of CAM2038 q1w at different injection sites (Group 1), and following multiple monthly SC administrations of CAM2038 q4w (Group 2 and Group 3), and to evaluate relative bioavailability of BPN following SC administration of 160 mg CAM2038 q4w as compared with 24 mg SL BPN (Group 3) in opioid-dependent subjects with a history of chronic non-cancer pain. The study will involve 4 phases: Screening, Treatment, open label safety extension and Follow-up.

Medical and eligibility screening will occur within approximately 21 days of the Treatment Phase. At Screening, subjects will provide written informed consent to participate in the study before any protocol-specified procedures or assessments are completed. The Screening visit will include standard medical screening procedures, complete medical/psychosocial history, brief substance abuse history and treatment history, clinical laboratory assessments, urine toxicology, as outlined in Table 1 (Group 1), Table 2 (Group 2), and Table 3 (Group 3). Subjects will be eligible for further participation if they meet all of the inclusion criteria and do not meet any of the exclusion criteria (as outlined in Section 8.1 and Section 8.2).

Subjects will remain on their daily SL BPN dose (24 mg/day) throughout the Screening phase. The last SL BPN dose will be taken on Day -1 (i.e., the day before the first CAM2038 dose). On Day 1, eligibility will be confirmed and up to approximately 40 eligible subjects will be randomized to either CAM2038 q1w (Group 1) or 128 mg CAM2038 q4w (Group 2). An additional group of 16 subjects was added following completion of randomization to Groups 1 and 2, in order to evaluate a higher dose of CAM2038 q4w (160 mg) after initial daily treatment with SL BPN (Group 3); therefore, these subjects will be enrolled, but not randomized. After enrollment/randomization, subjects will be administered CAM2038 SC injection depot formulation (all Groups) and SL BPN (Group 3) and monitored for at least 3 hours to ensure that the CAM2038 and SL BPN products are tolerated.

Subjects will be treated as follows:

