### **10.5.1 Adverse Events and Serious Adverse Events**

#### **Adverse Event Reporting** 10.5.1.1

Throughout the study, AEs will be documented on the appropriate page of the CRF whether or not considered treatment-related. This includes any new signs, symptoms, injury or illness, including increased severity of previously existing signs, symptoms, injury, or illness. CAM2038 injections sites will be examined during each scheduled visits for any signs of adverse site reactions, including erythema, pruritus, edema, pain, etc. The new injection site will also be examined shortly minutes after each injection to determine if any site related AEs have occurred. Subjects will also be queried specifically about local tolerability AEs in connection to the examinations.

Conditions existing prior to dosing will be recorded as part of the subject's medical history. The Investigator is responsible for assessing the relationship of AEs to the study drug; relationship will be classified as not related, unlikely related, possibly related, or probably related (see Section 10.5.1.2 for definitions).

All AEs and SAEs will be collected by the Investigator from the time informed consent is signed until 7 days after the EOT visit. This includes any AEs that are ongoing at the completion/termination of the study, and any AEs that start after the last dose of study drug. SAEs and AEs that have been designated as possibly related to study drug will be followed until resolution or stabilization. Any SAEs considered related to study drug should be reported to the Sponsor without regards to these timelines.

Any SAE, including death resulting from any cause, which occurs to any subject participating in this study or within 14 days of the EOT visit or premature discontinuation from the study whether or not related to the study drug, must be reported via email, facsimile or telephone within 24 hours of first being advised of the SAE. Follow-up information collected for any initial report of an SAE must be reported to the Sponsor or designee within 24 hours of receipt by the Investigator. In the event discussion is necessary call the Medical Monitor.

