## **11.4** ADVERSE EVENTS

Each AE and SAE term recorded on the case report forms (CRFs) by primary system organ class (SOC) and will be mapped to a preferred term using the MedDRA dictionary. The investigator will assess AE severity and relationship to the study treatment.

A treatment emergent adverse event (TEAE) is defined as any AE with an onset date on or after date of randomization (Groups 1 and 2) or first SL BPN dose (Group 3), or any ongoing event on the date of first dose that worsens in severity after date of randomization. Only TEAEs with an onset date prior to date of last dose + 30 days will be tabulated in summary tables. For the purpose calculating treatment emergence and inclusion in summary tables, incomplete onset dates will be imputed as detailed in Appendix A.

TEAEs will be summarized by the number and percent of subjects in each primary SOC and preferred term. Subjects will be counted only once for each primary SOC and each preferred term. Summary tables of TEAEs by primary SOC, preferred term and intensity will be provided. If a subject has more than one TEAE coded to the same preferred term, the subject will be counted only once for that preferred term by using the event with the highest intensity. Similarly, if a subject has more than one TEAE within a primary SOC category, the subject will be counted only once in that SOC category by using the event with the highest intensity. TEAEs by primary SOC, preferred term and relationship to study drug will be provided as well. If a subject has more than one TEAE coded to the same preferred term, the subject will be counted only once for that preferred term by using the most related event. Similarly, if a subject has more than one TEAE within a primary SOC category by using the most related event. In addition, serious adverse events (SAE) by primary SOC and preferred term will be provided. Deaths and SAEs will be summarized similarly to AEs. All adverse event tables will also include the total number of events, counting multiple events per subject.

Injection related TEAEs, Other (non-injection related) TEAEs as well as all TEAEs will be presented by treatment group and overall. Summaries of these TEAE subsets will be presented for the following categories:

- Study drug related
- Intensity
- Relationship to injection
- Serious
- AEs which led to discontinuation
- SAEs which led to discontinuation
- TEAEs occurring in 5% or greater of any treatment group (by preferred term)

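### SAP Appendix A can date an AE that ended before Day 1 after its own stop date and count it as treatment-emergent; its randomization anchor does not exist for Group 3.

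*SAP*

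**What the plan says.** SAP 11.4 defines a TEAE as "any AE with an onset date on or after date of randomization (Groups 1 and 2) or first SL BPN dose (Group 3"), or an event ongoing at first dose that worsens after randomization. Incomplete onset dates are resolved through Appendix A before this test is applied.

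In the adverse-event part of Appendix A (SAP 15.1), four routes lead to Day 1:

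- Onset wholly missing: "If onset date is completely missing, onset date is set to date of randomization".
- Month missing: "If year = year of randomization, then set month and day to month and day of randomization".
- Day missing, year equal to the randomization year: "If month = month of randomization then set day to day of first dose".
- Anything else: "For all other cases, set onset date to date of randomization".

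The remaining branches do not go to Day 1. For an earlier month in the same year, the rule is "If month < month of first dose then set day to last day of month". Earlier years also stay pre-dose, and later dates go to the first of the month or 1 January. No AE branch refers to the stop date. The end-date rules that close the appendix follow the concomitant medication and medical history heading and set no limit on AE onset.

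Protocol 10.5.1.1 states: "All AEs and SAEs will be collected by the Investigator from the time informed consent is signed". Protocol 7.1 allows about 21 days of screening and says of Group 3: "therefore, these subjects will be enrolled, but not randomized". SAP 4.2 confirms that Group 3 was not randomized. Protocol 12.3.5 leaves missing AE dates to the SAP, so no other rule applies.

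**The concern.** Moving an uncertain onset to first dose is reasonable when nothing else is known. Here something else may be known. If the stop date lies before Day 1, the event was over before study drug was given. The imputed record is then impossible, and the event enters the TEAE tables although Protocol 10.5.1.2 requires a TEAE to appear, worsen or recur after treatment starts. A screening event on the subject's own SL BPN could be tabulated as an event on study drug.

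The second problem is separate. SAP 11.4 gives Group 3 its own TEAE start, the first SL BPN dose, but Appendix A was not adapted. Safety is a secondary objective and Group 3 is the only 160 mg group, so its TEAE table should not depend on how a programmer fills a missing reference date.

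**Working it through.** The plan gives no figure to reproduce on this point, so the check applies the rule literally.

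**1. Worked example.** Take Day 1 = 20 June 2016 and an AE with recorded stop date 10 June 2016.

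| Onset as recorded | Appendix A onset | TEAE as written? | Onset capped at stop date |
|---|---|---|---|
| wholly missing | 20 June 2016 | yes | 10 June, not a TEAE |
| 2016 only | 20 June 2016 | yes | 10 June, not a TEAE |
| June 2016 | 20 June 2016 | yes | 10 June, not a TEAE |
| May 2016 | 31 May 2016 | no | unchanged |
| 2015 only | 31 Dec 2015 | no | unchanged |

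In the first three rows the imputed onset is 10 days after the event ended.

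**2. How often the missing-day branch reaches Day 1.** If Day 1 is calendar day d, then min(d−1, 21) of the 21 screening days lie in the same month. Averaging min(d−1, 21)/21 over a month of L days, with Day 1 uniform, gives:

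- L = 28: (231 + 6×21)/(21×28) = 357/588 = 0.607
- L = 30: (231 + 8×21)/(21×30) = 399/630 = 0.633
- L = 31: (231 + 9×21)/(21×31) = 420/651 = 0.645

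Here 231 is the sum of 0 to 21 for d = 1 to 22; each later day adds 21.

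**3. Literal run of the algorithm.** Day 1 was placed on each of the 366 days of 2016, with true onset on each of Days −21 to −1 and a complete stop date of Day −1. That gives 366×21 = 7,686 cases, all resolved before dosing.

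| Onset information | Counted as TEAE, as written | With onset capped at stop date |
|---|---|---|
| none | 7,686 (100%) | 0 |
| year only | 7,455 (97.0%) | 0 |
| month and year | 4,914 (63.9%) | 0 |

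The year-only exceptions are the 7,686 − 7,455 = 231 cases whose onset falls in the previous calendar year. All these percentages are conditional on the stated missingness pattern and on a pre-dose stop. They are not rates among all AEs.

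**4. Weight of one case.** Planned sizes are 20 to 24 in Group 1 and about 16 in each of Groups 2 and 3. One subject is 1/24 = 4.2%, 1/20 = 5.0% or 1/16 = 6.25%. SAP 11.4 tabulates preferred terms reaching 5% in any group. One false TEAE therefore suffices at n = 16 and at n = 20; at n = 24 it takes two subjects (2/24 = 8.3%).

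**5. Group 3.** The wholly missing case and the catch-all assign the date of randomization. The missing-month and missing-day cases first compare with the year of randomization. First dose appears only inside the branch already conditioned on that year, and it is not said whether it means SL BPN (Day 1) or CAM2038 (Day 8). So no AE branch can be executed as written for Group 3.

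**The case against.** Imputing an uncertain onset to first dose is a common conservative convention that guards against missing real TEAEs. The error needs three things together: an incomplete onset in a Day 1 branch, a true onset in screening, and a known stop before Day 1. Protocol 10.5.1.1 also sends conditions existing before dosing to medical history, and source verification should keep incomplete dates rare. Safety is descriptive: SAP 11.0 says there is no pre-specified safety outcome. For Group 3, SAP 11.4 names the first SL BPN dose in the same paragraph that invokes Appendix A, so the intended anchor can be inferred.

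Much of this stands. It limits the size and leaves no effect on the primary PK results. It does not remove the defect. Conservatism addresses unknown timing, whereas a pre-dose stop date settles it. The medical-history sentence reduces the pool, but the same section collects AEs from consent. An inferable Group 3 anchor is still not a stated one.

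Some stronger readings are tempting but unsupported:

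- A reader might take 61% to 65% as the share of screening AEs misclassified. It is only the share of screening days falling in Day 1's calendar month.
- A reader might assume that every false case adds 4.2 to 6.3 percentage points to its term. SAP 11.4 counts a subject once per preferred term, so a case adds nothing if that subject has a genuine TEAE with the same term.
- A reader might infer that Group 3 loses events while Groups 1 and 2 gain them. That depends on how software treats a missing randomization date, which the documents do not say.

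**Conclusion.** The point holds within limits. In the four Day 1 branches, an AE with a recorded stop before Day 1 is given an onset after its stop and counted as a TEAE. Onsets placed in an earlier month or year are handled correctly. The number affected cannot be derived from the documents and is probably small; in groups of this size a single case can still change which terms reach the 5% table. For Group 3 the rule is not executable as written, and no direction of error can be claimed.

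The conditional percentages assume uniform onset over 21 days, uniform Day 1 over the year and a complete stop date. The subject percentages assume planned enrolment. This should be corrected, but it is a safety-tabulation matter and does not threaten the study's main conclusions.

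**What to change.** 1. In Appendix A, and in the worsening clause of SAP 11.4, replace randomization by first dose of any study drug, meaning SL BPN on Day 1 for Group 3, as SAP 11.4 already does for TEAE start. Groups 1 and 2 are randomized on Day 1 before dosing (Protocol 9.3), so on-schedule subjects in those groups are unaffected.
2. Add: if the stop date, or the latest date compatible with a partial stop date, is before first dose, the AE is not treatment-emergent. Its onset is set to the earlier of the Appendix A date and that stop date.
3. Add: if the stop date is missing, or is partial and compatible with a stop on or after first dose, keep the conservative imputation to first dose. With Day 1 on 20 June, a stop recorded as May is pre-dose, while a stop recorded only as June keeps the conservative rule.

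The cost is SAP wording and matching program logic, with no new data and no design change. Because SAP 9.3 allows Groups 1 and 2 to be locked and analysed first, the revision should be in place before that lock.
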